8.6 Statistical Methods

The approach to handling missing data for efficacy analyses is described in Section 8.6.1. A summary of the analysis strategy for efficacy variables is shown in [Table 14](#). Nominal p-values may be computed for some efficacy analyses as a measure of strength of the association but no tests of hypotheses are planned in this estimation study. The analysis strategy for safety is described in Section 8.6.2.

8.6.1 Statistical Methods for Efficacy Analyses

This section describes the statistical methods that address the primary and secondary objectives.

Missing Values

A missing data point for a given study visit may be due to any of the following reasons: a visit occurred but data were not collected or were unusable; a visit did not occur; or a subject discontinued from the study before reaching the visit. Subjects who prematurely discontinued the assigned treatment are encouraged to remain in the study for follow-up, if possible.

The HCV RNA outcome is categorized as TND (Target not detected), TD(u) (Target detected but unquantifiable), and TD(q) (Target detected, quantifiable). There are 3 types of missing data handled by different approaches.

Type 1 is intermittent missing:

- Intermittent missing: If a missing data point is immediately preceded and followed by non-missing HCV RNA outcomes, the missing value would be imputed to the worst outcome of the two. For example, if a missing data point is preceded by TD(q) and followed by TD(u) or TND, then the missing value would be imputed as TD(q); if a missing data point is preceded by TD(u) and followed by TND, then the missing value would be imputed as TD(u); when a missing value is flanked by 2 TNDs, then the missing value would be imputed as TND.

Type 2 and 3 are both non-intermittent missing, but differ regarding their relationship to the study drug:

- Type 2 – Non-intermittent missing related to the study drug: For missing values due to premature study discontinuations due to treatment related reasons either for safety or efficacy, the missing values will be considered as treatment failures.
- Type 3 – Non-intermittent missing unrelated to the study drug: For missing data due to premature study discontinuations with reasons unrelated to treatment such as loss to follow-up, protocol violation, withdrawal of consent, administrative reasons, etc., the missingness mechanism is unlikely to be related to subjects' response to the HCV treatment, and therefore the missing at random (MAR) assumption is reasonable. The approaches to address this type of missing data depend on the analytical strategy, and these are described as follows.

The following 2 approaches will be used to handle non-intermittent missing data (Type 2 and 3) due to premature discontinuations, depending on the analytical strategy, as described in the following section and [Table 14](#) Analysis Strategy for Efficacy Variables.

- Treatment-Related Discontinuation = Failure (TRD=F) approach: The treatment related type 2 missing will be considered as failure; whereas the subjects who have the type 3 missing value and do not have virologic failure during the observed study period will be excluded from the analysis for the time points following their study withdrawal. Note that subjects with documented virologic failure during the treatment or follow-up period, even if they withdrew prematurely due to reasons not related to study drug, are classified as failures.
- Missing=Failure (M=F) approach: Any non-intermittent missing (i.e., type 2 and 3 missing) will be imputed as failure, regardless of the reason for study discontinuation.

In addition, a missing baseline/Day 1 HCV RNA result will be replaced with a screening result throughout all analyses, if available.

Proportion of Subjects With Virologic Responses

For the primary efficacy analysis based on the FAS population to estimate the proportions of subjects achieving SVR₁₂, 95% confidence intervals for these rates will be calculated using the Clopper-Pearson method [32] within treatment arms with no stratification. The missing data approach of M=F described above will be utilized for the primary analysis. The same method will be used to analyze all binary endpoints based on the FAS population.

The SVR₁₂ rates and confidence intervals for the randomized treatment-naïve F0-F2 subjects who received either 8 weeks of treatment or 12 weeks of treatment will be interpreted in the context of the historical clinical experience with EBR/GZR.

Sensitivity analyses will be performed for the primary endpoint and key secondary endpoint using the mFAS population with the TRD=F missing data approach. Under the assumption of missing completely at random (MCAR), the mFAS population excludes subjects who did not experience virologic failure, but prematurely withdraw from study due to reasons not related to the study drug (i.e., the subjects with the type 3 missing value). Note that subjects with documented virologic failure during the treatment or follow-up period, even if they withdrew prematurely due to reasons not related to study drug, are included in the mFAS population and classified as failures.

[Table 14](#) summarizes the key efficacy analyses and [Table 15](#) includes additional information on criteria to assess the primary endpoint (SVR₁₂) and key secondary endpoint (SVR₂₄).

Table 14 Analysis Strategy for Efficacy Variables

Endpoint/Variable (Description, Time Point)	Primary vs. Supportive Approach	Statistical Method	Analysis Population	Missing Data Approach
Primary				
Proportion of subjects achieving SVR ₁₂ in each treatment arm	P	95% CI (Clopper-Pearson)	FAS	M=F
Proportion of subjects achieving SVR ₁₂ in each treatment arm	S	95% CI (Clopper-Pearson)	mFAS	TRD=F
Secondary				
Proportion of subjects achieving SVR ₂₄ in each treatment arm	P	95% CI (Clopper-Pearson)	FAS	M=F
Proportion of subjects achieving SVR ₂₄ in each treatment arm	S	95% CI (Clopper-Pearson)	mFAS	TRD=F
CI = confidence interval; M=F = Missing=Failure; P = Primary approach; S = Secondary approach; TRD=F = Treatment-Related Discontinuation=Failure.				

Table 15 Analysis Populations, Criteria for Response, Non-Response, and Exclusion from Analysis Population

Analysis Population	Criteria for Response	Criteria for Non-Response	Criteria for Exclusion From Analysis Population
FAS	HCV RNA < LLOQ	HCV RNA \geq LLOQ	Subject did not receive at least one dose of study medication
mFAS	HCV RNA < LLOQ for baseline infection [†]	HCV RNA \geq LLOQ for baseline infection	Subject discontinued from the study for non-treatment related reasons. Examples include: Loss to follow-up; d/c due non-drug related AEs; informed consent withdrawal.

FAS = full analysis set; HCV = hepatitis C virus; LLOQ = lower limit of quantification; mFAS = modified full analysis set; RNA = ribonucleic acid.

[†] This includes the case where HCV RNA \geq LLOQ but is demonstrated to be due to reinfection (after clearance of baseline infection)

Subject Virologic Failure: Non-response, Rebound, Virologic Breakthrough and Relapse

Summary statistics will be provided to describe the rates of occurrence of subject non-response, rebound, virologic breakthrough, and relapse. Definitions for subject virologic non-response, rebound, breakthrough, and relapse are in Section 4.2.3.1.1.2.

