4.2.3.1.1 Measurement of HCV RNA

HCV RNA levels in plasma will be measured on blood samples drawn from each subject at various time points prior to, during, and after dosing, as indicated in the Trial Flow Chart (Section 6.0). Samples are collected and processed as per instructions provided by the central laboratory manual (assay type indicated in central laboratory manual).

Results from the sample collected at the screening visit are used to determine eligibility. Samples collected at other time points are used for efficacy analyses. They are also used to identify subjects who meet virologic failure criteria.

The nomenclature detailed in [Table 9](#) will be used when describing HCV RNA levels:

Table 9 Nomenclature for Describing HCV RNA Levels

Abbreviation	Definition	HCV RNA Level
TND	Target not detected	HCV RNA not detected
TD(u)	Target detected but unquantifiable	HCV RNA < LLOQ
TD(q)	Target Detected, quantifiable	HCV RNA \geq LLOQ

4.2.3.1.1.1 Definition of Efficacy Endpoints

Efficacy will be defined at different time points during the trial. Specific endpoints are:

- SVR₁₂ (sustained virologic response 12 weeks after the end of all study therapy). The subject has HCV RNA < LLOQ (either TD[u] or TND) 12 weeks after the end of all study therapy.
- SVR₂₄ (sustained virologic response 24 weeks after the end of all study therapy). The subject has HCV RNA < LLOQ (either TD[u] or TND) 24 weeks after the end of all study therapy.

4.2.3.1.1.2 Definition of Virologic Failure: Non-Response, Rebound, Virologic Breakthrough and Relapse

Lack of efficacy at different time points in the trial will be categorized as:

- Non-response: Subject has HCV RNA detected at end of treatment without HCV RNA $<$ LLOQ on treatment (note that breakthrough is captured below).
- Rebound: Subject has a rebound defined as $>1 \log_{10}$ IU/mL increase in HCV RNA from nadir while on treatment and confirmed from a separate blood draw within 2 weeks.
- Virologic breakthrough: Subject has a confirmed HCV RNA \geq LLOQ (TD [q]) after being $<$ LLOQ previously while on treatment. Confirmation is defined as an HCV RNA \geq LLOQ from a separate blood draw repeated within 2 weeks.
- Relapse: Subject has a confirmed HCV RNA \geq LLOQ (TD [q]) following end of all study therapy, after becoming undetectable (TND) at end of treatment. Confirmation is defined as an HCV RNA \geq LLOQ from a separate blood draw repeated within 2 weeks.

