¹⁴ Subjects in Arm 1 (8-week treatment arm) will proceed to FU4 as TW8 is their EOT visit. Subjects in Arm 2 (12-week treatment arm) will proceed to FU4 as TW12 is their EOT visit.

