8.5 Analysis Populations

8.5.1 Efficacy Analysis Population

The Full Analysis Set (FAS) population will serve as the primary population for the analysis of efficacy data in this study. The FAS population consists of all subjects who were assigned to a treatment arm and received at least one dose of study treatment.

A supportive analysis using the modified Full Analysis Set (mFAS) population will be performed for the primary (SVR_{12}) and key secondary efficacy endpoint (SVR_{24}). The mFAS population is a subset of the FAS, with subjects excluded for study discontinuation (lost to follow-up) with reasons unrelated to the treatment regimen. Examples of reasons for the exclusion of a subject include: failure to receive at least one dose of study treatment; loss to follow-up; missing data due to death with reasons unrelated to the study drug; discontinuation due to non-drug related AEs; informed consent and withdrawal.

Resistance Analysis (RA) Population will be used for resistance-associated variants (RAVs) analysis. The RA population is a subset of FAS, who either achieved SVR_{12} or met criteria for virologic failure (see Section 4). The RA does not include any subject who discontinued the study for reasons other than virologic failure. Baseline RAV analyses will be conducted in subjects for whom baseline sequencing data was available. Post-baseline RAV analyses will be limited to subjects who had both baseline and post-failure sequence data.

Details on the approach to handling missing data are provided in Section 8.6.1.

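### The intermittent-missing rule is not confined to one side of the end of treatment, so a missed end-of-treatment sample can label a cured Arm 1 subject a non-responder or leave a relapser in either arm with no failure category

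*Combined protocol and SAP*

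**What the plan says.** - **Imputation rule (Section 8.6.1, Missing Values, Type 1).** When a missing HCV RNA result has an observed result immediately before and after it, "the missing value would be imputed to the worst outcome of the two". The section's own example assigns TD(q) to a gap that has TD(q) before it and TND after it. The scope is any visit: "A missing data point for a given study visit may be due to any of the following reasons", and the reasons include unusable samples. The Missing=Failure approach covers only Types 2 and 3, so it does not displace this rule.
- **Schedule (Section 6.0, footnote 14).** "Subjects in Arm 1 (8-week treatment arm) will proceed to FU4 as TW8 is their EOT visit". For the 12-week arm the same footnote makes week 12 the last on-treatment visit, again with FU4 next. After Day 1, the only scheduled on-treatment sample before EOT in Arm 1 is week 4. Arm 2 has weeks 4 and 8.
- **Failure definitions (Section 4.2.3.1.1.2).** Non-response: "Subject has HCV RNA detected at end of treatment without HCV RNA" below LLOQ at any time on treatment. No confirmatory draw is required. Relapse: confirmed TD(q) after therapy, "after becoming undetectable (TND) at end of treatment". Rebound, breakthrough and relapse all need confirmation.
- **Where the labels are used.** Section 8.6.1 reports rates of the four failure categories. Section 8.5.1 builds the Resistance Analysis (RA) population from FAS subjects "who either achieved SVR_{12} or met criteria for virologic failure". Section 3.2 makes emergent RAVs in subjects without SVR a secondary objective.

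**The concern.** The worse-of-two rule is sensible when both neighbours describe the same state, for example a missed FU12 between FU4 and FU24. A missed EOT sample is different: one neighbour is on treatment and the other is after it. In Arm 1 the value is filled from week 4 and FU4. Week 4 may be too early to show clearance that came later, and FU4 may already show relapse. Neither then describes the end of treatment.

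At stake are the failure-category rates and the membership of the RA population. Few failures are expected, so one wrong label is visible in a table used to judge an 8-week regimen.

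**Working it through.** **Plan's own figures.** The claim disputes no stated number. As a check, the Clopper-Pearson limits for 45/50 reproduce at 78.2% and 96.7%, and all 13 rows of Table 17 reproduce to 0.1 point. Coding the Type 1 rule as the maximum over TND < TD(u) < TD(q) returns the category in each of the section's examples.

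**Enumeration.** Every category pattern with EOT missing was passed through the Type 1 rule and then the failure definitions. The true EOT state was taken as TND and follow-up TD(q) as confirmed. Arm 1 (week 4, FU4, FU12) has 3 × 3 × 3 = 27 patterns. Arm 2 (weeks 4 and 8, FU4, FU12) has 81. Pattern counts are not probabilities.

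| Observed pattern, EOT missed | EOT imputed | Label as written | SVR12 |
|---|---|---|---|
| (a) Arm 1: week 4 TD(q); FU4 and FU12 below LLOQ | TD(q) | Non-response, 4 of 4 patterns | Yes |
| (b) Either arm: TND on treatment; FU4 and FU12 TD(q) | TD(q) | None | No |

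- **Case (a).** The imputed value counts as detected at EOT and no on-treatment value is below LLOQ, so non-response is met. In Arm 2 this needs TD(q) at both week 4 and week 8.
- **Case (b).** The TND-at-EOT condition fails, so it is not relapse. An on-treatment value was below LLOQ, so it is not non-response. An imputed value has no confirmatory draw, so it is not breakthrough or rebound. With neither SVR12 nor a failure category, the subject is outside the RA population.
- **All true-relapse patterns.** With FU4 TD(q), the relapse label is lost in 9 of 9 patterns (Arm 1) and 27 of 27 (Arm 2). With FU4 below LLOQ and FU12 TD(q), it is lost in 5 of 6 and 15 of 18.

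**Size.** The documents give no rate of missed EOT samples and no rate of TD(q) at week 4. Assume 2–5% and 5–25%, independent.

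- False non-responders in Arm 1: 50 × 0.02 × 0.05 = 0.05, to 50 × 0.05 × 0.25 = 0.63.
- Lost relapses: Table 3 lists 1 relapse among 56 TN subjects (12 weeks, no RBV) and 2 among 37 TE subjects (all regimens). 120 × 0.02 × 1/56 = 0.04, to 120 × 0.05 × 2/37 = 0.32. The top end applies the TE rate to everyone. With the target mix of 100 TN and 20 TE, expected relapses are 100 × 1/56 + 20 × 2/37 = 2.9, and 2–5% of these is 0.06 to 0.14.
- Failures of any kind: 100 × 2/56 + 20 × 5/37 = 3.6 + 2.7, about 6.
- One false non-responder moves the Arm 1 rate from 0/50 (upper limit 7.1%) to 1/50 (2.0%, upper limit 10.6%). Both limits are in Table 18.

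**The case against.** The strongest reply is that failure labels were meant to use measured samples only. Section 4.2.3.1.1 describes collected samples as the means of identifying failures. Three of the four categories require a separate confirmatory draw. Section 8.6.1 speaks of documented failure, and Table 14 assigns missing-data approaches only to SVR12 and SVR24. On that reading case (a) disappears. But it is an inference: non-response is the one category without a confirmation requirement, and no section excludes imputed values.

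That reading does not rescue case (b). If EOT is simply left missing, the subject still cannot satisfy TND at EOT. So part of the objection stands: the relapse definition in Section 4.2.3.1.1.2 is itself a cause, and an observed TD(u) at EOT falls into the same gap.

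Two stronger readings are tempting.

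- **That case (b) turns relapses into on-treatment failures.** It does not for a subject seen below LLOQ on treatment, who gets no category at all. A non-response label arises only if no on-treatment value was below LLOQ.
- **That the cured subject in case (a) distorts the resistance results.** That subject is in the RA population through SVR12 anyway, counts as a success in the baseline RAV analysis, and has no post-failure sequence to contribute.

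The visit window for weeks 8 and 12 (−7 to +14 days) should also keep missed EOT samples uncommon.

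**Conclusion.** Wrong as written, and minor. Taken literally, the Type 1 rule together with the failure definitions mislabels a cured Arm 1 subject in case (a). In case (b) it leaves a relapser in either arm unclassified and outside the RA population, and there the relapse definition contributes.

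A reader might infer that the primary result is affected. It is not: SVR12 and SVR24 are decided by FU12 and FU24, and do not change when those are observed.

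Expected numbers are below one subject for each route: about 0.05–0.6 false non-responders in Arm 1 and 0.04–0.3 lost relapses in 120, against about 6 failures. These figures rest on the assumed missed-sample and week 4 rates, and on applying Table 3 rates from other durations and, for TE subjects, RBV-containing regimens. The point deserves correction because the affected categories are so sparse, and because a lost relapser is exactly the kind of subject the resistance objective needs.

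**What to change.** For analysis labels only, with no change to any rule applied in the clinic, add to Section 8.6.1:

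1. Type 1 imputation applies only when both neighbouring values are on treatment or both are after the last dose.
2. Imputed values do not count toward any virologic failure category, and non-response needs an observed EOT value.
3. When EOT is missing, confirmed TD(q) after treatment is classified as relapse if the last observed on-treatment value was below LLOQ. The subject then stays in the RA population.

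Carrying the last on-treatment value into a missed EOT is not an adequate substitute. It restores relapse after a TND value, but all 4 cured Arm 1 patterns with week 4 TD(q) remain non-responders.

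The text should also name a category for one remaining pattern: last on-treatment value TD(q), EOT missing, TD(q) after treatment. Virologic failure of undetermined timing, kept in the RA population, would serve. It should also say how an observed TD(u) at EOT followed by confirmed TD(q) is labelled.

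The cost is a few sentences and no new data. Section 8.0 provides for a supplemental SAP before final database lock.

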4.2.1.2 Rationale for Study Population (F0-F2 Fibrosis, TN, and TE subjects)

Although current French National HCV Treatment Guidelines imply that therapy should be proposed for almost all patients with HCV infection, including cirrhotic, non-cirrhotic, TN, and TE patients, consideration of eligible candidate's accounts for practical limitations to treatment access, including budgetary constraints. Accordingly, treatment recommendations outlined in these guidelines entail prioritizing treatment in those TN and TE patients with stage 2 or higher fibrosis, i.e., those who are at higher risk of developing complications from liver disease if untreated. However, the guideline authors do point out that universal access to HCV treatment for all patients in France is a goal by 2025 and that gradual extension of treatment indications will be considered by health authorities [22]. All currently recommended regimens for HCV GT4 patients are at least 12 weeks in duration and as seen in [Table 4](#), the regimen with the most supporting evidence (ombitasvir [OBV]/PTV/r + RBV × 12 weeks) includes RBV. Thus evaluation of whether a shorter 8-week RBV-free regimen is a viable option in subjects with F0-F2 fibrosis is important as treatment expansion strategies aimed at the goal of universal access are developed. Furthermore, this trial proposes to evaluate 2 unique treatment arms, thus inclusion of a broad spectrum of GT4 subjects can aid in understanding the merits of these regimens relative to specific patient subgroups.

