GT Subtype	Frequency of GT Subtype among 81 isolates from France sequenced in ref [9] n (%)	Number of GT4 subtype replicons assayed	Range of EBR EC ₅₀ nM	GZR EC ₅₀ for GT1b in Con 1 replicon for reference (nM ± SD)
4a	41 (50.6%)	3	.0002-.003	.003 ± .001
4d	17 (21%)	2	.0004-.0005	.003 ± .001
4f	10 (12.3 %)	1	.0019	.003 ± .001
4k	3 (3.7%)	0	n/a	.003 ± .001
4g	2 (2.5%)	2	.072-.0006	.003 ± .001
4c	2 (2.5%)	0	n/a	.003 ± .001
4q	2 (2.5%)	1	.0005	.003 ± .001
4t	2 (2.5%)	0	n/a	.003 ± .001
4n	1 (1.2%)	0	n/a	.003 ± .001
4p	1 (1.2%)	0	n/a	.003 ± .001

The activity of both EBR and GZR against GT4a and 4d, which appear to be the most prevalent subtypes in France, is comparable to what is seen against GT1b. This similar potency *in vitro* does appear to correlate with *in vivo* efficacy. As demonstrated in [Table 7](#), the treatment response rate of 12 weeks of EBR/GZR in the pooled TN GT4 dataset [10] was similar to the response rate in the in the TN GT1b patients treated in PN035, a randomized, placebo-controlled study that included both cirrhotic and noncirrhotic subjects with HCV GT1, 4, and 6 infection [27].

Table 7 Treatment Response Rates After 12 Weeks of EBR/GZR in Treatment-Naïve Subjects

Regimen	Duration	SVR ₁₂ GT1b (PN035)	SVR ₁₂ GT4 (pooled analysis)
EBR/GZR	12 weeks	129/131 (99%)	54/56 (96%)

The comparable *in vitro* and clinical profiles of EBR and GZR in GT4 and GT1b infection suggest that efficacy of regimens not yet studied in TN GT4 patients may be similar to what was seen in GT1b infection. Accordingly, justification for the 8-week regimen proposed for TN GT4 subjects with F0-F2 fibrosis is based on the high efficacy observed when this same regimen was given to a similar GT1b population. In PN035, one of the treatment arms included an 8-week regimen of EBR and GZR in noncirrhotic TN subjects with GT1b infection and demonstrated that 28/29 TN GT1b subjects with F0-F2 fibrosis achieved SVR₁₂.

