5.3 Randomization or Treatment Allocation

In this open-label, partially randomized study, approximately 120 subjects will be enrolled. Approximately 75 (minimum of 60) TN subjects with stage 0-2 fibrosis will be randomized 2:1 to Arms 1 and 2, respectively. A total of approximately 45 TN subjects with stage 3-4 fibrosis and TE subjects with stage 0-4 fibrosis will be assigned (not randomized) to Arm 2. The treatment allocation ([Table 1](#)) will be implemented centrally using an interactive voice response system/integrated web response system (IVRS/IWRS).

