5.4 Stratification

The randomized subjects will be stratified by baseline HCV RNA viral load: less than or equal to 800,000 IU/mL and greater than 800,000 IU/mL.

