Statistical Methods for Key Efficacy/Immunogenicity/Pharmacokinetic Analyses	
A 2-sided 95% confidence interval (CI) based on Clopper-Pearson method will be constructed for the proportion of subjects achieving arm-specific SVR₁₂ and SVR₂₄, and for treatment naïve F0-F2 subjects achieving arm-specific SVR₁₂.
 
There will be no efficacy hypothesis testing conducted in this estimation study.

Statistical Methods for Key Safety Analyses	The proportion of subjects who experienced adverse events of elevated laboratory values that are reported as ECIs during the study therapy period will be estimated along with the corresponding 95% confidence intervals based on Clopper-Pearson method. In addition, the broad clinical and laboratory AE categories consisting of the percentage of subjects with any AE, a drug related AE, a serious AE, an AE which is both drug-related and serious, and who discontinued due to an AE will be summarized.
Interim Analyses	No interim analyses are planned for this study.
Multiplicity	There will be no multiplicity adjustments in the final analysis of this estimation study.
Sample Size and Power	
Approximately 120 subjects will be enrolled with approximately 50 in Arm 1 (8 week treatment) and 70 in Arm 2 (12 week treatment). The 95% CI and half-width of the 95% CI for SVR₁₂, under various scenarios, is presented in Table 17.
 
For example, when the sample size is 25, if the SVR₁₂ rate is 92.0% (23 successes out of 25), the exact 95% CI is (74.0%, 99.0%). When the sample size is 50, if the SVR₁₂ rate is 90.0% (45 successes out of 50), the exact 95% CI is (78.2%, 96.7%). When the sample size is 70, if the SVR₁₂ rate is 90.0% (63 successes out of 70), the exact 95% CI is (80.5%, 95.9%).

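### The one randomised comparison, 8 versus 12 weeks in TN F0-F2 subjects, has no planned difference or confidence interval

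*Combined protocol and SAP*

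**What the plan says.** Only TN F0-F2 subjects are randomised: 2:1 to 8 weeks (Arm 1, target 50, minimum 40) or 12 weeks (Arm 2, target 25, minimum 20), per Section 2.1 and Table 1. Section 5.4 adds: "The randomized subjects will be stratified by baseline HCV RNA viral load", with a cut at 800,000 IU/mL. The rest of Arm 2 is allocated directly. Section 5.3 says "approximately 45 TN subjects with stage 3-4 fibrosis and TE subjects with stage 0-4 fibrosis will be assigned (not randomized) to Arm 2".

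The planned efficacy analysis works one arm at a time:

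- Section 8.1: a two-sided 95% interval "will be constructed for the proportion of subjects achieving arm-specific" SVR12 and SVR24, and also for SVR12 in TN F0-F2 subjects.
- Section 8.6.1: the intervals "will be calculated using the Clopper-Pearson method [32] within treatment arms with no stratification". The rates for the randomised TN F0-F2 subjects "will be interpreted in the context of the historical clinical experience with EBR/GZR".
- Table 14: SVR12 and SVR24 by treatment arm. It has no row for TN F0-F2 subjects and none for a difference.
- Section 8.10: for randomised subjects, SVR12 by viral-load category and arm. Further summaries are optional and unnamed.
- Section 8.6: nominal p-values may be produced for some efficacy analyses, but no contrast or test is named.

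Sections 3.0 and 8.3 state that this is an estimation study without hypotheses.

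**The concern.** Section 4.2.1.2 gives the purpose of the short arm: "evaluation of whether a shorter 8-week RBV-free regimen is a viable option in subjects with F0-F2 fibrosis is important". The support for it in Section 4.2.2.1 is extrapolation, namely that "efficacy of regimens not yet studied in TN GT4 patients may be similar to what was seen in GT1b infection". The only 8-week result in the documents is that "28/29 TN GT1b subjects with F0-F2 fibrosis achieved" SVR12, which is a different genotype. In genotype 4 the documents give a TN result for 12 weeks only (54/56, Tables 3 and 7). It comes from pooled earlier studies and is not concurrent.

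The 12-week subjects randomised alongside the 8-week subjects are therefore the like-for-like genotype 4 reference. The trial creates that group by stratified randomisation, but the analysis plan never uses it as a comparator. A reader will set the two rates side by side anyway. Without a planned interval for the difference, similar rates may be read as equivalence, or an interval may be chosen after the data are seen.

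**Working it through.** **1. What the specified outputs give for the randomised subjects**

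| Quantity | 8 weeks | 12 weeks | Difference with CI |
|---|---|---|---|
| SVR12 | yes | yes (TN F0-F2 secondary endpoint) | not specified |
| SVR12 by viral-load stratum | yes | yes (8.10) | not specified |
| SVR24 | yes (Arm 1 is entirely TN F0-F2) | not specified | not specified |

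SVR24 is planned by whole arm only, and the Section 8.10 subgroups are for SVR12 only. Whole Arm 2 cannot stand in for the 12-week randomised group: 25 (TN F3-F4) + 20 (TE) = 45 of 70, and 45/70 = 64%.

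**2. Reproducing the plan's own figures**

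Clopper-Pearson limits for x/n are the 2.5% quantile of Beta(x, n-x+1) and the 97.5% quantile of Beta(x+1, n-x). All 13 rows of Table 17 reproduce within rounding. For example, 48/50 gives 86.3 to 99.5, 45/50 gives 78.2 to 96.7, and 24/25 gives 79.6 to 99.9. Table 17 describes single groups only.

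**3. The missing contrast**

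Let d be the 8-week minus the 12-week rate. The Miettinen-Nurminen limits are the values of d at which

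z(d) = (p1 - p2 - d) / sqrt{ [q1(1-q1)/n1 + q2(1-q2)/n2] × N/(N-1) } = ±1.96

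Here p1 and p2 are the observed rates, q1 and q2 are the maximum-likelihood rates under q1 - q2 = d, and N = n1 + n2.

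Lower limit for 48/50 vs 24/25, at d = -0.1032:

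- q1 = 0.8807 and q2 = 0.9839.
- Variance = (0.8807×0.1193/50 + 0.9839×0.0161/25) × 75/74 = 0.00277, so the SE is 0.0526.
- z = 0.1032/0.0526 = 1.96.

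The upper limit is found in the same way. Results in percentage points:

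| 8 weeks | 12 weeks | Difference | 95% CI |
|---|---|---|---|
| 48/50 | 24/25 | 0.0 | -10.3 to 16.1 |
| 45/50 | 24/25 | -6.0 | -18.4 to 10.6 |
| 38/40 (minimum n) | 19/20 (minimum n) | 0.0 | -12.7 to 19.4 |

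Crossing the five Table 17 counts at n=50 (45 to 49) with the three at n=25 (22 to 24) gives 15 combinations. The lower limit runs from -18.4 to -0.9 and the width from 25.1 to 33.5. Every interval includes zero.

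**4. Sensitivity to method**

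Newcombe's interval for 48/50 vs 24/25 is -10.0 to 15.8, and for 45/50 vs 24/25 it is -17.8 to 10.5. Both are close to the values above.

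**5. Stratified version**

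The documents give no stratum sizes. The assumption is that about 30% to 60% of subjects fall in the lower viral-load stratum (15/8, 20/10, 25/12 or 30/15 subjects in the 8-week/12-week groups), with every possible split of the failures between strata. Using Cochran-Mantel-Haenszel weights:

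- 48/50 vs 24/25: lower limit -11.6 to -9.8, upper limit 15.8 to 16.5.
- 45/50 vs 24/25: lower limit -20.6 to -17.5, upper limit 8.9 to 10.9.

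Stratifying moves a limit by at most about 2.2 points.

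**The case against.** The analysis delivers what the objectives ask for. Sections 3.1 and 3.2 ask for efficacy in each arm, no objective asks for a comparison, and Section 8.9 says the sample sizes were not set on statistical grounds. Whether 8 weeks is viable can be read as a question about the absolute 8-week rate, which the Arm 1 interval answers. The plan reports the randomised subgroup separately for SVR12, so a reader could compute an unstratified difference. The historical 12-week genotype 4 result of 54/56 has a Clopper-Pearson interval of about 87.7 to 99.6, tighter than 24/25 would give. An interval 25 to 34 points wide that includes zero may itself be misread as no difference. SVR24 is closely concordant with SVR12 (Section 4.2.3.1), so its absence in 25 subjects matters less.

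Much of this stands. The omission is a design choice and not a contradiction or an arithmetic error. The difference will be imprecise, and the choice between Miettinen-Nurminen and Newcombe hardly matters. But none of it supplies the contrast. The 54/56 result is pooled and non-concurrent, so it does not replace a randomised reference. A difference computed by readers would be unstratified and by a method picked after the fact, and for SVR24 no specified output allows it. The imprecision exists whether or not it is reported, and stating it guards against the misreading.

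**Conclusion.** The point holds. The plan randomises one comparison and specifies no estimate of it. It also omits the SVR24 rate in the randomised 12-week subjects. With equal observed rates of 96% at target enrolment, an 8-week deficit of about 10 points stays open (about 13 points with equal rates of 95% at minimum enrolment). The separate intervals of 86.3 to 99.5 and 79.6 to 99.9 do not show this.

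The planned within-arm analyses remain valid and no stated figure changes. This is an addition that should be made, not a flaw that invalidates the trial. The sizes rest on hypothetical responder counts taken from Table 17, or on 95% in both groups at minimum enrolment. The stratified figures also rest on assumed stratum shares.

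**What to change.** Add to Section 8.6.1 and Table 14, for randomised TN F0-F2 subjects in the FAS with missing counted as failure:

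- The 8-week minus 12-week difference in SVR12 and in SVR24, with a two-sided 95% Miettinen-Nurminen interval stratified by the randomisation factor (≤800,000 vs >800,000 IU/mL). Set a rule in advance for reverting to the unstratified interval when a stratum is sparse, for example fewer than 5 subjects in either arm.
- The SVR24 rate with its Clopper-Pearson interval by arm.
- A Table 14 row for the TN F0-F2 SVR12 endpoint, which Section 8.4.1.1 already lists.

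Label the difference descriptive, with no test and no margin. Keep the within-arm rates and the historical context. State in the plan and the report that the interval is expected to be about 25 to 34 points wide at target enrolment and cannot establish that 8 and 12 weeks are similar.

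The cost is SAP wording and a few table rows, with no new data, visits or subjects. Section 8.0 already allows changes before database lock through a supplemental SAP.
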